4.4.2. Handling of missing values in scales or summary parameters

Missing items in scales or summary parameters will be imputed to allow for the derivation of the total scale/parameter score. The appropriate imputation rules will be described in the sections where the total scores are defined.

4.4.3. Handling of missing values and early dropouts in the efficacy analyses during the first study period (up to Week 12)

This is for the “efficacy chapter 2” analysis.

For binary data (e.g., ACR20), two different imputations will be done for missing visits as well as early dropouts: non-responder imputation (NRI) and LOCF, up to and including Week 12. The NRI imputation will be primary, and LOCF will be secondary.

For other data (ordinal or continuous), missing visits as well as early dropouts will be imputed using the last observation carried forward (LOCF) algorithm, up to and including Week 12.

Definitions of the imputation methods:

- LOCF (all types of parameters, from binary to continuous): to impute a missing value, the last preceding nonmissing value will be used (which could even be a baseline value).
- NRI (binary response parameters only): to impute a missing response, the subject will be assumed to be a non-responder.

For all parameters, an observed-case analysis will also be performed (i.e., without any imputation). The observed-case analysis will serve as a sensitivity analysis (to ascertain the impact of early dropouts on the results) and will basically be limited to:

- ACR20/50/70/N: descriptive at W12+W24 and inferential at W12
- EULAR remission: descriptive at W12+W24
- SDAI/CDAI: descriptive at BSL+W12+W24
- DAS28: descriptive at BSL+W12+W24 and inferential at W12
- All ACR components (VAS, joint counts, CRP, HAQ-DI): descriptive at BSL+W12+W24
- QoL (FACIT,SF-36): descriptive at BSL+W12+W24.

4.4.4. Handling of missing values and early dropouts in the efficacy analyses during the study period as a whole (full 24 weeks)

This is for the “efficacy chapter 2” analysis.

For binary data (e.g., ACR20), two different imputations will be done for missing visits as well as early dropouts: non-responder imputation (NRI) and LOCF, up to and including Week 24. The NRI imputation will be primary, and LOCF will be secondary.

For other data (ordinal or continuous), missing visits as well as early dropouts will be imputed using the last observation carried forward (LOCF) algorithm, up to and including Week 24.

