For all parameters, an observed-case analysis will also be performed (i.e., without any imputation). This observed-case will not be shown for subjects who switched treatment. See previous section for the parts where the observed-case analysis will be presented.

As all subjects in the placebo arm switch to 100 mg q.d. as of Week 12, no placebo arm will be presented during the second part of the study.

4.4.5. Handling of missing values and early dropouts in the efficacy analyses during the second study period (after Week 12)

This is for the “efficacy chapter 3” analysis.

Subjects in this analysis must have data after the Week 12 potential treatment switch in dosing. Subjects who discontinued the study during the first period of the study will not be included in this analysis and will therefore also not be imputed.

For binary data (e.g., ACR20), two different imputations will be done for missing visits as well as early dropouts during period 2: non-responder imputation (NRI) and LOCF, up to and including Week 24. The NRI imputation will be primary, and LOCF will be secondary.

For other data (ordinal or continuous), missing visits as well as early dropouts during period 2 will be imputed using the last observation carried forward (LOCF) algorithm, up to and including Week 24.

Note that no Period 1 efficacy data will be carried forward into this chapter 3 analysis.

For all parameters, an observed-case analysis will also be performed (i.e., without any imputation).

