8.1. ACR20, ACR50, ACR70 AND ACR-N**8.1.1. Parameters**

ACR20 response when:

- $\geq 20\%$ improvement from baseline in SJC66, and
- $\geq 20\%$ improvement from baseline in TJC68, and
- $\geq 20\%$ improvement from baseline in at least 3 of the following 5 items:
 - Pain VAS (taken from the HAQ-DI)
 - Patient's Global Assessment of Disease Activity VAS
 - Physician's Global Assessment of Disease Activity VAS
 - Total HAQ-DI score
 - CRP.

Subjects who do not meet this criterion are non-responders.

If any of the 7 components of the ACR20 would be missing, then this missing component will be imputed using the value of the last preceding nonmissing visit. If all components are missing, then the derived ACR20 will remain missing. Imputation of such cases for the tables will be done there using LOCF or NRI like any other missing value.

Subjects who discontinue within the first week so that ACR20/50/70 responses cannot be determined will be classified as non-responders.

The ACR50 and ACR70 responses are derived using the same algorithm, but with 50% and 70% cutoffs respectively.

Note that the primary endpoint of the study is the ACR20 at Week 12 in the ITT population, using NRI imputation.

The ACR-N is derived using the following formula:

ACR-N = MIN [% improvement in TJC68, % improvement in SJC66, MED % improvement in (patient's global assessment, physician's global assessment, patient's assessment of pain, HAQ-DI, CRP)]

So this is taking the smallest of the percentage increases in SJC66, TJC68, and the third of the remaining 5 parameters. In case the ACR-N is negative (i.e., the subject actually worsens instead of improves), then the ACR-N is replaced by a 0. The ACR-N is therefore a number between 0 and 100.

The ACR-N represents the percentage NN% according to which the subjects would have been an "ACRNN" responder.

(See further sections on how to derive these components.)

The time to ACR20 response

= (date of first time ACR20 response is reached) – (date of first medication intake) + 1 day, if the subject achieved ACR20 response during the initial 12 weeks treatment period, or
= MIN (date of the Week 12 visit, date of trial termination) – (date of first medication intake) + 1 day, in case the subject did not achieve ACR20 response at any time during the initial 12 weeks treatment period.

Next to this, the visit during which the ACR20 response was first recorded will be analyzed as well:

- Week 1
- Week 2
- Week 4
- Week 8
- Week 12

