8.4. DAS28(CRP)

8.4.1. Parameters

$$\text{DAS28(CRP)} = 0.56 \times \sqrt{\text{TJC28}} + 0.28 \times \sqrt{\text{SJC28}} + 0.36 \times \text{Ln}[1 + \text{CRP (in mg/L)}] + 0.014 \times \text{patient's disease activity VAS (in mm)} + 0.96$$

(TJC28 and SJC28 are the 28 joint counts for tenderness and swelling. See further sections on how to derive these components. Ln = natural logarithm.)

DAS28(CRP) scores can only be derived when all components are nonmissing. If any of the components of the DAS28(CRP) would be missing, then this missing component will be imputed using the value of the last preceding nonmissing visit.

Note that if for a specific visit both the regular CRP as well as the high-sensitive CRP are available, the high-sensitive CRP will be used for the derivation of the DAS28(CRP).

Note that the percentage change from baseline remains missing if the baseline value itself equals zero.

Next to the actual DAS28(CRP) value, also the changes and percent changes from baseline will be derived.

Categorization of the DAS28(CRP) scores:

- High disease activity: > 5.1
- Moderate disease activity:] 3.2 , 5.1]
- Low disease activity: [2.6 , 3.2]
- Remission: < 2.6

A second categorization of the DAS28(CRP) into EULAR response categories (none, moderate, good) will be done according to the following:

Actual DAS28(CRP)	Improvement in DAS28(CRP) from baseline:		
	> 1.2] 0.6, 1.2]	≤ 0.6
≤ 3.2	Good	Moderate	None
] 3.2, 5.1]	Moderate	Moderate	None
> 5.1	Moderate	None	None

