8.7. ACR COMPONENT: HAQ-DI**8.7.1. Parameters**

The HAQ-DI consists of 20 individual items.

The pain VAS of the HAQ-DI is analyzed separately as component of the ACR20/50/70, not in this chapter on HAQ-DI.

The HAQ-DI total scores are:

- 8 domain subscales: dressing, arising, eating, hygiene, walking, reaching, grip, activities
- Overall total score

Derivation of these summary scores:

- There are four response options ranging from “Without any difficulty” to “Unable to do”, scored from 0 to 3.
- Step 1: Derive the 8 category scores by using the highest sub-category score from each domain.
- Step 2: Adjust for use of aids/devices and/or help from another person when indicated:
 - Adjust the score for a domain by increasing a 0 or a 1 to a 2.
 - If a patient's highest score for that sub-category is a 2 it remains a 2, and if a 3, it remains a 3.
- Step 3: Divide the summed domain scores by the number of domains answered to obtain a HAQ-DI score of 0-3 (3=worst functioning). There must be a nonmissing score for at least six of the eight domains. Otherwise a HAQ-DI score cannot be computed.

If any of the 20 items would be missing, then this missing component will be imputed using the value of the last preceding nonmissing visit.

The analysis will present the actual values, changes from baseline and percent changes from baseline.

Note that the percentage change from baseline remains missing if the baseline value itself equals zero.

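### SAP 4.4.5 bars Period 1 data from Chapter 3, but the component-filling rules have no period limit, so composites reported under 100 mg can contain placebo or 50 mg values

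*SAP*

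**What the plan says.** SAP 4.4.5 governs Chapter 3 and contains an unqualified note: "Note that no Period 1 efficacy data will be carried forward into this chapter 3 analysis". Its imputation rules address whole visits and dropouts. For ordinal and continuous data, "missing visits as well as early dropouts during period 2 will be imputed using the last observation carried forward (LOCF) algorithm"; for binary data NRI is primary and LOCF secondary.

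Partly missing scales are delegated by SAP 4.4.2: "The appropriate imputation rules will be described in the sections where the total scores are defined". Those sections say:

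- **ACR20/50/70 (8.1.1):** if one of the seven components is missing, "this missing component will be imputed using the value of the last preceding nonmissing visit". Only when all components are missing does the response stay missing, and then "Imputation of such cases for the tables will be done there using LOCF or NRI like any other missing value".
- **DAS28(CRP) (8.4.1):** "If any of the components of the DAS28(CRP) would be missing, then this missing component will be imputed using the value of the last preceding", that is, from the latest earlier visit with a value.
- **HAQ-DI (8.7.1):** "If any of the 20 items would be missing, then this missing component will be imputed using the value of the last preceding nonmissing visit".
- **Remission (8.2.1) and SDAI/CDAI (8.3.1):** the same rule.

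SAP 2.1 places Week 12 in Period 1. SAP 2.1.1 reports former placebo subjects and 50 mg non-responders in Chapter 3 columns labelled as switched to 100 mg.

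**The concern.** Read together, the two sets of instructions conflict for anyone whose treatment changes at Week 12. At Week 16, the first post-switch visit, the last preceding value of a component is normally the Week 12 one, measured on placebo or 50 mg. The filled composite is then tabulated as a response on 100 mg.

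Chapter 3 is the only efficacy analysis that uses switchers' data after Week 12, because Chapter 2 treats them as discontinued at that point (SAP 4.5.1). SAP 2.1.1 presents it as showing whether non-responders start to respond with longer treatment or a dose increase. The continuing 100 mg and 200 mg columns beside it cannot mix treatments in this way. The SAP also does not say which rule prevails, so two programmers could derive different Week 16 values from the same data.

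**Working it through.** The plan states no figure on this point. The check is a comparison of rules, then an illustration and a sizing on assumed values.

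**1. Order of operations.** SAP 8.1.1 derives the composite with filled components first and leaves LOCF or NRI for visits where everything is missing. The general comments in SAP 8 confirm that observed-case listings contain component-imputed values, which are flagged. Component filling therefore sits beneath NRI, LOCF and observed-case alike, while the 4.4.5 imputation text deals with whole visits.

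**2. What is exposed.** Exposed: ACR20/50/70 and ACR-N, remission, SDAI, CDAI, DAS28(CRP) and HAQ-DI items. Not exposed at item level: joint counts (8.5.1), FACIT (8.9.1) and SF-36 (8.10.1), which prorate or average within the visit. Weeks 20 and 24 are exposed only if that component has not been observed since the switch.

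**3. One hypothetical switcher, CRP missing at Week 16.** Assumed improvements: SJC66 40%, TJC68 35%, pain 30%, patient global 25%, physician global 10%, HAQ-DI 10%. Both joint criteria are met and two of the five other items reach 20%, so CRP decides.

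| Carried Week 12 CRP improvement | True Week 16 CRP improvement | ACR20 as derived | True ACR20 |
|---|---|---|---|
| 0% | 60% | No | Yes |
| 25% | 5% | Yes | No |

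For DAS28(CRP), assume TJC28 = 4, SJC28 = 3, patient global = 30 mm:

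- carried CRP 20 mg/L: 0.56×√4 + 0.28×√3 + 0.36×ln(21) + 0.014×30 + 0.96 = 4.08
- true CRP 5 mg/L: the same with ln(6) = 3.63

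The difference is 0.36×ln(21/6) = 0.45.

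**4. How many subjects.** If 1% to 10% of Week 16 visits were partly missing, 0.01×70 = 0.7 to 0.10×70 = 7 former placebo subjects would be affected. That caps the effect at 1 to 10 percentage points if every outcome flipped the same way. If instead each of seven components were missing independently with probability m, the share of visits with some but not all missing is 1 − (1 − m)^7 − m^7: 6.8%, 19.2% and 30.2% for m = 1%, 3% and 5%. These shares count visits with a carried value, not changed outcomes.

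**5. Effect of a look-back limit on ACR20 under NRI.** With the limit, a response is scored only when the observed components already guarantee one. The current rule scores a response in all those cases, plus any where the carried value passes the threshold. The denominator is the same, so the NRI rate under the limit cannot exceed the current rate.

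A simulation of Week 12 joint-count non-responders agrees. Assumptions: mean improvement 10% on placebo, SD 40, on-drug gain 25 points, correlations 0.5 between components and between visits, true Week 16 ACR20 about 36%.

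| m | Bias, current rule | Bias, limit plus NRI |
|---|---|---|
| 1% | about −0.6 points | about −0.9 points |
| 3% | about −1.9 | about −2.8 |
| 5% | about −3.1 | about −4.5 |

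Raising the gain to 35 points or the between-component correlation to 0.7 kept this ordering.

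**6. Effect on continuous composites.** When components are missing at random in the same simulation setting, leaving the composite missing gives bias of about zero. Filling from Week 12 pulls the mean toward the pre-switch level.

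**The case against.** **The note may override.** The 4.4.5 sentence is unqualified and specific to Chapter 3, so it can be read as governing all carry-forward there. Read as visit-level only, it is compatible with the separately delegated component rules. Both readings are possible, but neither closes the gap. If the note overrides, the SAP has no rule for a partly observed Week 16 ACR response, and 8.3.1 and 8.4.1 require every component of SDAI, CDAI and DAS28(CRP). If it does not override, its plain statement is untrue.

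A reader might also infer more than the documents support:

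- **That ACR20 on 100 mg is biased down and a look-back limit would recover it.** Downward bias in the non-responder columns is plausible under the assumptions above, but single errors go either way, and a simulated Week 12 responder column rose by under 1 point. Under NRI, the primary method, the limit lowers the rate further.
- **That a 50 mg switcher missing both joint counts at Week 16 is wrongly failed by the carried values.** By definition at least one Week 12 joint count improved by less than 20%, so the carried values do fail the criterion. With the limit the subject is still a non-responder: either the other five components already fail, or the response is undeterminable and NRI applies. Nothing is gained.
- **That the Chapter 3 observed-case tables at Week 16 are contaminated.** The Chapter 3 table specifications restrict observed-case output to Weeks 12 and 24, despite the broader general comment in SAP 8. Only Week 24 could be affected, and only if the component was never observed after the switch.
- **That the size is established.** Independent missingness across components collected at one visit is an assumption that favours a large effect. A joint count goes missing only when more than half the joints are unassessed, and HAQ-DI needs six of eight domains.

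**Conclusion.** The inconsistency is real. Followed as written, the component rules put pre-switch measurements into Chapter 3 composites labelled 100 mg, which 4.4.5 says will not happen. The effect is concentrated at Week 16 and confined to partly observed visits of switched subjects.

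No size can be derived from the documents. The figures above rest on assumed missingness, means and correlations, and realistic values are probably at the low end. Chapter 3 is descriptive only (SAP 4.5.3), and the Week 12 ACR20 analysis does not depend on any of this. This is a minor specification defect. The statistical gain from correcting it lies in the continuous composites; for the binary outcomes under NRI the gain is consistency only.

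**What to change.** Add to SAP 4.4.5, with a cross-reference in 8.1.1, 8.2.1, 8.3.1, 8.4.1 and 8.7.1, for Chapter 3 derivations in subjects whose treatment changed at Week 12:

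- A missing component or HAQ-DI item is filled only from a visit after the switch.
- If there is none, DAS28(CRP), SDAI and CDAI stay missing at that visit. HAQ-DI is scored from the items and domains answered, under the existing six-of-eight-domain rule.
- ACR20/50/70 and remission are derived from the observed components where these settle the outcome. Otherwise they stay missing in the LOCF and observed-case outputs and count as non-response under NRI.
- The number of such undeterminable cases is reported per column and visit.

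The note in 4.4.5 should also say whether component filling from Week 12 remains allowed for subjects who stay on the same treatment. There it breaches the letter of the note but mixes no treatments.

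Cost: SAP wording and one extra condition in the derivation programs. Downside: a few more missing Week 16 composites, and an NRI rate in the switched columns that is the same or slightly lower.

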4.4.6. Handling of missing values and early dropouts in the safety analysis

No imputation is done of missing values or missing visits. The analysis will be observed-case only.

4.5.3. In the efficacy and safety analysis of the second study period

The treatment arms will be presented descriptively only, as separate columns.

In the safety analysis, this only applies to the adverse events where the treatment-emergent AEs that emerge during the second part of the study will be presented separately. The lab data, ECG and vital signs are already presented in chapter 2 of the analysis.

4.6. HANDLING OF OUTLIERS

All measured values will be included in the analyses.

4.7. HANDLING OF SECONDS IN DATETIME FIELDS

If a datetime field contains seconds, these will be cut off (i.e., rounded down to the minute) prior to data analysis. The analysis will only use the date and time up to the minute.

4.8. STRATIFICATION FACTORS

In case there is a discrepancy in randomization stratification stratum between IWRS and the actual eCRF data, then:

1. The actual eCRF stratum will be used in analyses and analysis models, and
2. Any such discrepancy will be flagged in the listing on randomizations (listing 16.2.1.1).

5. SOFTWARE AND PROCEDURES

5.1. SOFTWARE

SAS version 9.3 (or higher) will be used for programming.

5.2. PROCEDURES

Analyses will comply with ICH regulations, in particular: (ICH-E3) , (ICH-E6) and (ICH-E9).

The following Galapagos SOPs will be followed:

- SOP-CLI-001: Developing Clinical Study Documents (version 1.0)
- SOP-CLI-003: Managing Data Processing Activities (version 1.0)
- SOP-CLI-004: Managing DSMB Activities (version 1.0)

The following ████ STAT SOPs will be followed:

Location	Document Type	Document Number	Effective Date	Document Title
Global	SOP	03.002.01	03-Feb-2014	Providing Statistical Input to CSRs and Clinical Summaries for Submission Dossiers
Global	SOP	03.003.00	06-Feb-2012	Generation of define.xml
Global	SOP	03.004.01	03-Feb-2014	Statistical Input to Clinical Trial Protocols
Global	SOP	03.005.00	29-Mar-2012	Planning and Conducting Interim Analyses
Global	SOP	03.007.01	01-Oct-2013	Development of a Statistical Analysis Plan
Global	SOP	03.009.01	01-Oct-2013	Quality Control of SAS® Programming
Global	SOP	03.010.01	01-Oct-2013	Development of SAS® Programs
Global	SOP	03.011.00	30-Apr-2012	Randomization and Unblinding
Global	SOP	03.012.02	02-Dec-2013	Biostatistics and Statistical Programming Directory Structure Creation and Setup
Global	SOP	03.013.01	01-Oct-2013	Development and Production of Analysis Datasets
Global	SOP	03.014.01	29-Apr-2014	Biostatistics and Statistical Programming Functional Lead Responsibilities
Global	SOP	03.015.01	29-Apr-2014	Performing Blind Review of Data

5.3. FORMATS

Derived data will be following CDISC ADaM 2.1 (ADaMIG 1.0) format.

Tables, listings and figures will follow the Mock TLFs, as provided in a separate document.

6. STATISTICAL METHODS

6.1. PLANNED ANALYSES, PROTOCOL AMENDMENTS INCLUDED

6.1.1. Demographic and other baseline characteristics

Subject disposition including the reasons for study termination will be tabulated.

Demographic characteristics will be listed. Demographic characteristics will be summarized using appropriate descriptive statistics, as applicable.

6.1.2. Efficacy Variables

6.1.2.1. Definition of primary efficacy endpoint: ACR20 at Week 12

The primary endpoint is the percentage of subjects achieving an ACR20 response at Week 12. Other time points will be regarded as secondary endpoints. The non-responder imputation (NRI) of the ACR20 will be the primary parameter, with observed-case and last observation carried forward (LOCF) imputation as secondary confirmatory analyses.

The ACR response is a measurement of improvement in multiple disease assessment criteria. The ACR20 response is defined as:

≥20% improvement from baseline in SJC66 (66 joints) and TJC68 (68 joints)

AND

≥20% improvement from baseline in at least 3 of the following 5 assessments

- Pain (VAS) in cm (from HAQ-DI).
- Patient's Global Assessment of Disease Activity (VAS) in cm.
- Physician's Global Assessment of Disease Activity (VAS) in cm.
- Patient's Assessment of Physical Function as measured by HAQ-DI.
- CRP in mg/L.

6.1.2.2. Definition of secondary efficacy endpoints

ACR50 and ACR70

ACR50 and ACR70 are similarly defined as ACR20, except the improvement threshold from baseline is 50% and 70%, respectively.

ACR-N

The ACR-N is the smallest percentage improvement in swollen and tender joints and the median of the remaining 5 core parameters, and is expected to be more sensitive to change than the ACR20, ACR50 or ACR70. It is a number varying between 0 and 100.

ACR-N = MIN [%improvement in TJC68, %improvement in SJC66, MED %improvement in (patient's global assessment, physician's global assessment, patient's assessment of pain, HAQ-DI, CRP)], cut off at 0 in case it would be a negative number.

ACR/EULAR Remission

A subject's disease activity status can be defined as being in remission if:

when scores on the TJC28, SJC28, CRP (actual value in mg/dL) and Patient Global Assessment of Disease Activity (cm) are all ≤1.

Simplified Disease Activity Index (SDAI)

The SDAI is the numerical sum of 5 outcome parameters: TJC28, SJC28, Patient Global Assessment of Disease Activity (in cm), Physician's Global Assessment of Disease Activity (in cm), and CRP (mg/dL).

$$\text{SDAI} = \text{TJC28} + \text{SJC28} + \text{Patient's Global Assessment of Disease Activity (VAS in cm)} + \text{Physician's Global Assessment of Disease Activity (VAS in cm)} + \text{CRP (mg/dL)}$$

The SDAI can be categorized:

- High disease activity: $\text{SDAI} > 26$
- Moderate disease activity: $]11, 26]$
- Low disease activity: $]3.3, 11]$
- Remission: ≤ 3.3

Clinical Disease Activity Index (CDAI)

The CDAI is the SDAI modified to exclude CRP.

$$\text{CDAI} = \text{TJC28} + \text{SJC28} + \text{Patient's Global Assessment of Disease Activity (VAS in cm)} + \text{Physician's Global Assessment of Disease Activity (VAS in cm)}$$

The CDAI can also be categorized:

- High disease activity: > 22
- Moderate disease activity: $]10, 22]$
- Mild disease activity: $]2.8, 10]$
- Remission: ≤ 2.8

Disease Activity Score 28 Joints Based on CRP (DAS28[CRP])

The DAS28(CRP) is a statistically derived index combining tender joints (28 joints), swollen joints (28 joints), CRP and Patient's Global Assessment of Disease Activity (general health, GH).

DAS28(CRP) is defined as follows:

$$\text{DAS28(CRP)} = 0.56 \times \text{SQRT}(\text{TJC28}) + 0.28 \times \text{SQRT}(\text{SJC28}) + 0.36 \times \text{Ln}(\text{CRP}+1) + 0.014 \times \text{GH} + 0.96,$$

Where:

- TJC28 is 28 joint count for tenderness
- SJC28 is 28 joint count for swelling.
- $\text{Ln}(\text{CRP}+1)$ is the natural logarithm of (CRP value [mg/L] + 1)
- SQRT is square root
- GH is the Patient's Global Assessment of Disease Activity on a 100 mm VAS

Categorization of the DAS28(CRP) scores:

- High disease activity: > 5.1
- Moderate disease activity: $] 3.2, 5.1]$
- Low disease activity: $[2.6, 3.2]$
- Remission: < 2.6

EULAR Response

A second categorization of the DAS28(CRP) will be done according to the following table:

Actual DAS28(CRP)	Improvement in DAS28(CRP) from Baseline		
	> 1.2	$]0.6, 1.2]$	≤ 0.6
≤ 3.2	Good	Moderate	None
$]3.2, 5.1]$	Moderate	Moderate	None
> 5.1	Moderate	None	None

Quality of Life: FACIT Fatigue Scale and SF-36

Quality of life will be assessed using the FACIT fatigue scale and the SF-36 questionnaire. The appropriate (sub)totals will be derived according to the scale's scoring algorithm.

